## 11.2. Assessment of Safety

Adverse events (AEs) will be monitored from the start of this extension study (informed consent provided by patient at the Baseline visit) until 30 days after administration of the last dose of study drug (end of study drug taper-off). Treatment-emergent adverse events (TEAEs) will be summarized with respect to overall incidence, as well as severity and relationship of the AEs to the study drugs. AEs that result in dose modification, discontinuation of the study drug, or serious adverse events will also be summarized

AEs with onset after the initiation of study drug and within 30 days after the last dose of study drug may be considered treatment-emergent. This will include any AE with onset prior to initiation of study drug that increased in severity during the treatment period. All reported AEs including those with onset more than 30 days after the last dose of study drug will be included in the data listings.

Abnormal changes in laboratory parameters that are not disease-related will be monitored and recorded throughout the study.

All adverse events will be encoded according to MedDRA 8.0. Treatment emergent adverse events (TEAE) will be analyzed, i.e. all adverse events starting or worsening between start of long-term extension study up to 30 days after end of study drug taper-off. Incidences on preferred term and body system basis will be calculated for all TEAEs.

Different categories for causality will be recorded in the CRFs, and these 4 categories (DEFINITE, PROBABLE, POSSIBLE, and NOT RELATED) are defined in Section 11.3 (Criteria for Determining Relationship to Study Drug) of this protocol.

In addition, all SAEs and all AEs leading to premature discontinuation will be presented as separate listings. TEAE from both studies (double-blind and open-label extension) will be combined, i.e. each patient will be counted just once (with patient's respective TEAE).

Other safety evaluations, such as vital signs, physical and neurological examinations, laboratory variables, ECG variables, post-void residual bladder ultrasound, and AUA symptom index will be analyzed descriptively.

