## 11. STATISTICAL MEASUREMENTS, EVALUATIONS AND ANALYTICAL METHODS

### 11.1. Assessment of Efficacy

Monthly total seizure rates will be calculated for the entire open-label part of Study VRX-RET-E22-304 and described statistically. Monthly total seizure rates observed during the open-label extension period will be compared to the monthly total seizure rates observed during the Baseline phase of the double-blind study VRX-RET-E22-302. The percent change in monthly total seizure rates from the Baseline phase will be classified into <0, [0, 25), [25, 50), [50, 75), [75, 100] and described. The responder rate during the open-label study (defined as a reduction in seizure frequency  $\geq 50\%$ ) will also be summarized using descriptive statistics.

The number of seizure free days, in percent to the individual duration of the open-label treatment, will be calculated and summarized using descriptive statistics. This percentage will be classified into [0, 25), [25, 50), [50, 75), [75, 95), [95, 100), [=100] and described statistically.

All-cause withdrawal rates will be calculated as a percentage and respective "times to event" will be described by a Kaplan-Meier survival curve. Specific reasons for withdrawal will also be described separately.

This is an open-label extension study with the emphasis on safety. Efficacy is not the primary objective of this study unlike the double-blind study VRX-RET-E22-302. Descriptive statistics of efficacy measures such as number of patients, mean, standard deviation, median, minimum and maximum will be provided for continuous variables. The number and percentages in each category will be presented for categorical data. The pairwise t-test will be used to assess whether the retigabine treatment remains effective in the open-label extension study if necessary. The pairwise t-test may be sorted by the geographic region [Central/Eastern Europe vs. Rest of World (ROW)]. The safety assessments will use essentially the same descriptive statistics and pairwise t-test as mentioned above for efficacy. The complete details of efficacy analyses will be described in the Statistical Analysis Plan.

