## 11.2. Assessment of Safety

Adverse events (AEs) will be monitored from the start of this extension study (informed consent provided by patient at the Baseline visit) until 30 days after administration of the last dose of study drug (end of study drug taper-off). Treatment-emergent adverse events (TEAEs) will be summarized with respect to overall incidence, as well as severity and relationship of the AEs to the study drugs. AEs that result in dose modification, discontinuation of the study drug, or serious adverse events will also be summarized

AEs with onset after the initiation of study drug and within 30 days after the last dose of study drug may be considered treatment-emergent. This will include any AE with onset prior to initiation of study drug that increased in severity during the treatment period. All reported AEs including those with onset more than 30 days after the last dose of study drug will be included in the data listings.

Abnormal changes in laboratory parameters that are not disease-related will be monitored and recorded throughout the study.

All adverse events will be encoded according to MedDRA 8.0. Treatment emergent adverse events (TEAE) will be analyzed, i.e. all adverse events starting or worsening between start of long-term extension study up to 30 days after end of study drug taper-off. Incidences on preferred term and body system basis will be calculated for all TEAEs.

Different categories for causality will be recorded in the CRFs, and these 4 categories (DEFINITE, PROBABLE, POSSIBLE, and NOT RELATED) are defined in [Section 11.3](#) (Criteria for Determining Relationship to Study Drug) of this protocol.

In addition, all SAEs and all AEs leading to premature discontinuation will be presented as separate listings. TEAE from both studies (double-blind and open-label extension) will be combined, i.e. each patient will be counted just once (with patient's respective TEAE).

Other safety evaluations, such as vital signs, physical and neurological examinations, laboratory variables, ECG variables, post-void residual bladder ultrasound, and AUA symptom index will be analyzed descriptively.

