This study is the open-label extension of the Phase 3 Study VRX-RET-E22-302. VRX-RETE22-302 is a randomized, double-blind, placebo-controlled, parallel-group, multicenter, study of 900 mg/day and 600mg/day retigabine versus placebo. During the 4-week titration phase patients are titrated to the target dose. 510 patients are expected to be randomized to treatment. A 12-week maintenance phase follows. All patients who wish to enter the open-label extension protocol will enter a 4-week transition phase in which their dose will be titrated to 300 mg TID in order to maintain the blind to the maximum extent. Thereafter, the patients could enter this extension study (Study VRX-RET-E22-304). Patients who do not wish to enter the open-label extension protocol will have their dose tapered over a 3-week period.

This Statistical Analysis Plan (SAP) was created according to Protocol VRX-RET-E22-304, Amendment 1 (July 2, 2007).

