Probable	Temporal association, other etiologies are possible but unlikely. The event may respond if the study drug is discontinued.
Definite	Established temporal association with administration of the study drug with no other probable cause. The event should resolve when the study drug is discontinued and recur on re-challenge.

The intensity and relationship assessments to study drug are recorded on the AE CRF page.

Treatment-emergent AEs (TEAEs) will be tabulated, i.e., those events which are not present at baseline or worsened in severity following the start of treatment. Any adverse events starting more than 30 days after the last administration of study drug will not be tabulated.

The onset date of an adverse event will be compared to the date of first dose of study medication in this extension study to determine if the adverse event is treatment emergent

or not. Adverse events with an onset date on or after the date of first dose of study medication will be classified as treatment emergent.

The following adverse event summaries will be provided:

- A summary of the number and percentage of patients reporting a treatment emergent adverse event by body system, and preferred term
- A summary of the number and percentage of patients reporting a treatment emergent adverse event by maximum intensity, body system and preferred term
- A summary of the number and percentage of patients reporting a treatment emergent adverse event by relationship to study drug, body system and preferred term
- A summary of the number and percentage of patients reporting a treatment emergent adverse event leading to dose modification by body system and preferred term

For each patient and each adverse event, the worst severity recorded will be attributed and used in the by-severity summaries. Similarly, the worst causality (most related to treatment) will be attributed and used in the by-causality summaries. If severity or causality are missing, the worst case will be assumed.

The date the AE started should be well collected in CRF data. However, in the unlikely case that the AE start date is missing, the AE date will imputed be as follows.

Scenarios			Imputed AE Onset Date
Day	Month	Year	
missing			
If the month and year of the AE are the same as the month and year of the first dose date in the extension, use the day of the first dose date.
 
Otherwise use 1 for day.

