#### 4.8 Changes in the Conduct of the Study or Planned Analysis

No changes in the conduct of the study or planned analysis have occurred.

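### SAP 4.8 declares no change, yet the protocol's Kaplan-Meier curve of withdrawal and its combined 302+304 TEAE count are missing, and the TEAE date test has no branch for events that worsen

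*SAP*

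**What the plan says.** SAP 4.8 states: "No changes in the conduct of the study or planned analysis have occurred". SAP section 1 names Protocol Amendment 1 of 2 July 2007 as its basis. In that amendment, and again in Amendment 2, Protocol 11.1 says that times to all-cause withdrawal "will be described by a Kaplan-Meier survival curve", and Protocol 11.2 says "TEAE from both studies (double-blind and open-label extension) will be combined, i.e. each patient will be counted just once". Neither sentence carries a condition.

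For withdrawal, SAP 4.1.1 plans counts by primary reason (Table 1), descriptive statistics for days to discontinuation (Table 2) and a listing. The only figure in SAP section 8 concerns seizure frequency. The adverse-event shells have a single retigabine column.

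On treatment emergence, Protocol 11.2 counts "all adverse events starting or worsening between start of long-term extension study up to 30 days after end of study drug taper-off" and adds that an event with earlier onset qualifies if its severity increased on treatment. SAP 4.5.2 first defines TEAEs as "those events which are not present at baseline or worsened in severity following the start of treatment". Its next paragraph says that the onset date is "compared to the date of first dose of study medication in this extension study to determine if the adverse event is treatment emergent", and closes: "Adverse events with an onset date on or after the date of first dose of study medication will be classified as treatment emergent". Protocol 10.5 has adverse events still ongoing at the last Transition visit of Study 302 moved onto the extension's AE pages.

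**The concern.** A reader who relies on SAP 4.8 would not know that two promised analyses are absent. For a long-term tolerability study, the withdrawal curve is the output that handles unequal follow-up. Tables 1 and 2 do not account for patients still on treatment when the data are cut. The combined TEAE count is the only promised output that shows a patient's adverse events across both studies without double counting.

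The TEAE rule governs most of the adverse-event tables. A programmer could follow the definition sentence or the date test, and the two give different counts for events that began in Study 302 and worsened on open-label drug. A date test applied alone errs in one direction only: it lowers the TEAE count.

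**Working it through.** **Omitted analyses.** Each protocol commitment was compared with SAP section 4, the lists of tables, figures and listings (SAP 7 to 9) and the shells.

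- *Kaplan-Meier curve of all-cause withdrawal* (Protocol 11.1, both amendments). The SAP has Tables 1 and 2 and no survival method or curve. SAP 4.8 does not declare this.
- *Combined 302+304 TEAEs, each patient once* (Protocol 11.2 and synopsis, both amendments). SAP 4.5.2 anchors TEAEs to first dose in the extension, and no combined table is listed. SAP 4.8 does not declare this.

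So two of two are absent and neither is declared.

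**TEAE rule.** Take an event with onset in Study 302, mild at entry to the extension and severe after the first open-label dose.

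- Protocol 11.2: treatment emergent, because severity increased.
- SAP 4.5.2, definition sentence: treatment emergent, because it worsened.
- SAP 4.5.2, date test: not met, because onset precedes first extension dose.

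The date-imputation table in SAP 4.5.2 supplies onset dates only, so it adds no worsening branch.

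**Where such an event would still appear.** SAP 4.5.2 promises a summary of patients with any adverse event, but SAP section 7 lists no all-AE incidence table, and Table 15 is TEAE. Tables 16 and 21 are titled for adverse events without the treatment-emergent qualifier, whereas SAP 4.5.2 and 4.5.3 describe those summaries as TEAE. Listings 14 and 17 are titled treatment-emergent, although SAP 4.5.3 promises all withdrawals and all serious events. Only the all-AE listing (Listing 11) is certain to contain it.

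**Table 2, illustration only.** Suppose Table 2 covers discontinuers only, which the SAP does not say. Protocol 7.4 reports that in an earlier extension 18 of 222 patients stopped within 3 months and 41 of 222 within 6. With 30-day months (Protocol 10.1), three hazards fit those figures:

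- A, constant: −ln(1 − 41/222)/6 = 0.0340 per month.
- B, constant: −ln(1 − 18/222)/3 = 0.0282 per month.
- C, two-piece: 0.0282 to month 3, then −ln(181/204)/3 = 0.0399 per month.

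Let F(t) be the proportion discontinued by time t. With complete follow-up to T, the discontinuer-only median solves F(t) = 0.5 × F(T). For A at 12 months, F(12) = 33.5%, and F(t) = 16.8% gives t = 5.39 months = 162 days.

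| Hazard | 12 months | 24 months | 36 months | Ratio 36:12 | 12-month retention |
|---|---|---|---|---|---|
| A | 162 d | 288 d | 384 d | 2.37 | 66.5% |
| B | 165 d | 300 d | 409 d | 2.48 | 71.3% |
| C | 175 d | 296 d | 382 d | 2.19 | 64.2% |

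The median rises 2.2- to 2.5-fold with the underlying risk unchanged. With entry assumed uniform over 12, 18 or 24 months, and cuts at 24 and 36 months after first entry, the ratio is 1.44 to 1.65. A Kaplan-Meier curve would estimate the same 12-month retention at every cut that reaches 12 months of follow-up.

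**The case against.** **The date test may not exclude anything.** The classification sentence, read alone, gives a sufficient condition. It does not say that only such events qualify, and the definition naming worsening stands just above it. SAP 4.5.2 also says that the worst severity is taken when the same event carries two severities, which suggests that more than one severity entry per event was foreseen. This stands in part: a reader might infer that worsened events are certain to be excluded, and the documents do not establish that. But the worst-severity sentences grade an event and do not classify it. The SAP also presents the date comparison as what determines treatment emergence, and neither document says that worsening opens a new record with a new onset date.

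**Other omissions could be added to the list.** Fisher's exact test of TEAEs (Protocol 11.2), the comparison with Study 302 (synopsis), the pairwise t-test (Protocol 11.1) and the MedDRA version (8.0 in the protocol, 9.1 in the SAP) also differ. A reader might infer that all of these are missing safety evidence. The documents do not support that. All patients receive retigabine, so the groups for Fisher's test are undefined. The comparison with Study 302 is one synopsis sentence without endpoint or method. The t-test is to be used only if necessary, and SAP 4.5.2 states its MedDRA version openly. These are minor items to declare.

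**Retention can be read elsewhere.** Table 14 gives exposure in days and in bands to beyond 36 months, the cohort sizes in SAP 4.4 give crude retention, and Listing 1 gives each patient's status. This is useful, but Table 14 does not separate patients who stopped from those still on treatment, so it does not replace the curve.

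**The SAP predates Amendment 2.** This does not explain the omissions, because Amendment 1 contains both commitments.

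**Conclusion.** The point holds for two unconditional analyses and for the wording of the TEAE rule. The statement in SAP 4.8 is inaccurate against the SAP's own base version. The date test in SAP 4.5.2 conflicts with its own definition sentence and with Protocol 11.2. If programmed alone, it would undercount TEAEs among events carried over from Study 302, unless worsening is recorded as a new event. By how many cannot be derived from the documents.

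A reader might take the 2.2- to 2.5-fold rise as the error in Table 2. It is not an estimate of that. It holds only if Table 2 covers discontinuers only and if hazards extrapolated from six months of an earlier extension apply out to 36 months. Neither document schedules the cuts used.

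The omissions can be confirmed by direct reading. The effect of the TEAE wording is less certain, because it depends on how worsening is recorded. The study is descriptive and no decision rule rests on these outputs, so this should be fixed but does not undermine the trial.

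**What to change.** 1. In SAP 4.5.2, state one TEAE rule: onset on or after, or increase in severity after, the first open-label dose. Say how worsening of a carried-over event is recorded. Align the titles of Tables 16 and 21 with the text. Cost: wording, plus a check of the CRF convention.
2. Add the protocol's Kaplan-Meier curve of time to all-cause withdrawal from first open-label dose, censoring patients still on treatment at the data cut. Keep Tables 1 and 14, and state the denominator and time origin of Table 2. Cost: one figure from data already planned.
3. Correct SAP 4.8 to list each dropped or changed analysis with its reason. Either restore the combined TEAE table or say where it is reported. Restoring it is the costlier route: Study 302 adverse events must be merged, coded to one MedDRA version, and de-duplicated against the transferred events. A cross-reference needs only wording.
4. In the same section, declare Fisher's exact test (or define its groups), the comparison with Study 302, the conditional t-test and the MedDRA version. Cost: wording.

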4.5.3 Deaths, Serious Adverse Events, and Other Significant Adverse Events

A serious adverse event (SAE) is any AE occurring at any dose that results in any of the following outcomes:

- Death
- Is a life-threatening experience. Life-threatening means that the patient was, in the view of the investigator, at immediate risk of death from the event as it occurred
- Requires in-patient hospitalization or prolongation of existing hospitalization. Hospitalization for elective treatment or a pre-existing condition that did not worsen during the clinical investigation is not considered an AE.
- Results in a persistent or significant disability/incapacity (i.e., a substantial disruption of a person’s ability to conduct normal life functions). Disability is defined as a substantial disruption in a person’s ability to conduct normal life functions
- Results in a congenital anomaly/birth defect

Important medical events that may not result in death, be life threatening, or require hospitalization may be considered SAEs only when they jeopardize the health of the patient or require medical or surgical intervention to prevent one of the outcomes listed in the above definition. If there is any doubt whether the information constitutes an SAE, the information is treated as an SAE in this study.

The following adverse event summaries will be provided:

- A summary of the number and percentage of patients reporting a fatal treatment emergent adverse event by body system, and preferred term
- A summary of the number and percentage of patients reporting a serious treatment emergent adverse event by body system, and preferred term
- A summary of the number and percentage of patients reporting a treatment emergent adverse event leading to withdrawal from the study by body system and preferred term

The following adverse event listings will also be provided:

- A by-patient listing of all deaths that occurred during the study
- A by-patient listing of all serious adverse events
- A by-patient listing of all adverse events leading to withdrawal

#### 4.5.4 Clinical Laboratory Evaluation

All clinical laboratory assessments are implemented by a central laboratory.

The clinical laboratory data were collected at baseline, Months 1, 3, 6, 9, 12, 16, 20, 24, 28, 32, and 36. Additional hematological assessments are collected at Months 2, 4, 8 and 10.

The laboratory data include:

1. Hematology: hemoglobin, hematocrit, RBC count, WBC count with differential, and platelet count.
2. Blood chemistries: sodium, potassium, chloride, bicarbonate, glucose, cholesterol, creatinine, calcium, phosphorus, BUN, uric acid, total bilirubin, total protein, AST, ALT, and alkaline phosphatase levels.
3. Routine urinalysis: specific gravity, pH, protein/albumin, glucose/sugar, ketones/acetone, and hemoglobin/blood. In order to standardize measurements, Bayer multistix 8-SG or equivalent dipsticks will be used.
4. Microscopic urinalysis: RBC, WBC, casts, and crystals/cells.

Descriptive statistics for laboratory results and change from baseline for each visit will be presented separately for hematology, biochemistry and urinalysis parameters. The number of patients with clinically significant liver function tests will also be presented.

A by-patient listing of all laboratory data will also be provided with abnormal values highlighted, and including centre, patient identifier, age, sex, race, weight and visit. A listing of the central laboratory reference ranges will also be provided.

#### 4.5.5 Vital Signs, Physical Findings and Other Observations Related to Safety

##### 4.5.5.1 Vital Sign Measurements

Vital sign measurements, including supine and standing measurements of systolic blood pressure (mmHg), diastolic blood pressure (mmHg), pulse (bpm), weight (kg), and oral

temperature (°C), are collected at each visit during the open-label extension with the exception of the haematological evaluation visits (Months 2, 4, 8 and 10).

Descriptive statistics for vital sign results and change from baseline for each visit will be presented.

The number of patients with orthostatic hypotension will also be presented. Orthostatic hypotension is defined as either a systolic blood pressure decrease of  $\geq 20$  mmHg upon standing or a diastolic blood pressure decrease of  $\geq 10$  mmHg upon standing.

A by-patient listing of all vital sign measurements will also be provided.

#### 4.5.5.2 ECG

The ECG parameters assessment includes heart rate, PR interval, QRS interval, QT interval, and QTc interval.

QT intervals will be corrected using both Bazett's and Fridericia's formulas. For purposes of data analysis, Fridericia's QT correction will be considered as primary. The QT interval and QTc interval data will be presented both as analysis of central tendency (e.g. means, medians) and categorical analyses.

Categorical analysis of QT/QTc interval data are based on the number and percentage of patients meeting or exceeding the limit value that is defined in ICH guideline E14, i.e. Absolute QTc interval prolongation if QTc interval  $>450$ ,  $>480$ , or  $>500$  msec and Change from baseline in QTc interval  $>30$  or  $>60$  msec.

A listing of patients meeting or exceeding the highest limit value, i.e. QTc interval  $>500$  msec or change from baseline in QTc interval  $>60$  msec, will be provided. The listing of patients will include the dose of study medications that the patient was taking on the day prior to the ECG reading.

Descriptive statistics for QT/QTc intervals will be first presented in the tables. The number and percentage of patients for the QT/QTc category in ICH guideline E14 will be presented in the tables, and the patients who have significant QT/QTc measures will be provided in the listings. The means and standard deviations of QT/QTc intervals by week and the patient with significant QT/QTc changes will be also presented in the tables.

A by-patient listing of all ECG data will also be provided.

